6.10 Duration of Follow-up

Patients will be followed for local recurrence, distant recurrence, and toxicity for 12 months after surgery (or date of definitive end of treatment for patients who do not have surgery). Follow-up visits will be include the following:

- 3-month follow-up: H&P, ECOG PS.
- 6-month follow-up: CT C/A/P, blood for ctDNA.
- 12-month follow-up: CT C/A/P

6.11 Lost to Follow-Up

A participant will be considered lost to follow-up if he or she fails to return for 3 scheduled

visits and is unable to be contacted by the study team.

The following actions must be taken if the participant fails to return to clinic for a required study visit:

- The study team will attempt to contact the participant and reschedule the missed visit within 1 month and counsel the participant on the importance of maintaining the assigned visit schedule and ascertain if the participant wishes to and/or should continue in the study.
- Before a participant is deemed lost to follow-up, the investigator or designee will make every effort to regain contact with the participant (where possible, 3 telephone calls and, if necessary, a certified letter to the participant's last known mailing address). These contact attempts should be documented in the participant's medical record or study file.
- Should the participant continue to be unreachable, he or she will be considered to have withdrawn from the study with a primary reason of lost to follow-up.

7.0 DOSE DELAYS/DOSE MODIFICATIONS

7.1 **Dosing Adjustments for Radiation Therapy**

Radiotherapy for this trial may take place over a maximum of 10 business days before it is considered a protocol deviation. There are no dose adjustments (reductions, omissions) associated with radiotherapy.

7.2 **Dosing Adjustments for Chemotherapy**

Dose reductions and holds for chemotherapy may be made at the discretion of the treating physician. All chemotherapy is being given as per standard of care, and dosing is not dictated by this protocol. Please refer to the package insert of each drug for recommended dosing adjustments.

8.0 **REGULATORY AND REPORTING REQUIREMENTS**

The entities providing oversight of safety and compliance with the protocol require reporting as outlined below. Please refer to Appendix B for definitions and Appendix C for a grid of reporting timelines. All investigators treating patients on this study are responsible for ensuring that serious adverse events (as defined in Appendix B) are reported to the WUSM PI within an adequate timeframe for the event to be assessed by the WUSM PI for reporting to HRPO and QASMC.

Adverse events will be tracked from baseline through 12 months after surgery (or, for patients who do not undergo surgery, 12 months after definitive end of treatment). All adverse events must be recorded on the toxicity tracking case report form (CRF) with the exception of:

• Baseline adverse events, which shall be recorded on the medical history CRF

• Adverse events that are thought to be at least possibly related to a non-protocol treatment received after the patient comes off SCRT or neoadjuvant chemotherapy

Refer to the data submission schedule in Section 11 for instructions on the collection of AEs in the EDC.

Reporting requirements for Washington University School of Medicine study team may be found in Section 8.1. Reporting requirements for secondary site study teams participating in WUSM-coordinated research may be found in Section 8.2.

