3.0 OBJECTIVES AND ENDPOINTS

Objectives	Endpoints	Justification for Endpoints
Primary		•
To quantify the pCR rate in gastric cancer patients treated with preoperative radiation	The rate of pCR (both ypT and ypN) in gastric cancer patients treated with	A complete pathologic response may result in improved oncologic
followed by total neoadjuvant chemotherapy.	preoperative radiation followed by total neoadjuvant chemotherapy.	outcomes. High rates of pCR may lead the way for future studies of non- operative management of gastric cancer.
Secondary		
To quantify the proportion of patients able to complete a full course of total neoadjuvant chemotherapy	Proportion of patients able to complete a full course of total neoadjuvant chemotherapy.	Evaluating the feasibility of total neoadjuvant therapy will help guide future trials seeking to maximize response prior to surgery.
To quantify the local control rate of gastric cancer patients treated with preoperative radiation followed by chemotherapy.	The local control rate at 1 year post RT.	Providing radiation therapy prior to chemotherapy and surgery may increase the local control rate.
To quantify the toxicity of gastric patients treated with preoperative radiation followed by chemotherapy.	The rate of grade 3 or greater toxicity as defined by CTCAE v 5.0.	Adding radiation therapy to chemotherapy and surgery may increase the toxicity associated with treatment.
To quantify the overall survival in gastric cancer patients treated with preoperative radiation followed by chemotherapy.	The overall survival at 1 year post RT.	By improving local control and pCR, overall survival may be improved.
To quantify the disease free survival in gastric cancer patients treated with preoperative radiation followed by chemotherapy.	The disease-free survival at 1 year post RT.	By improving the local control, disease free survival (locoregional and distant recurrence) may be improved as well.
Tertiary/Exploratory		
To quantify the deviation in dose to the tumor due to variation in stomach position.	Average percent difference in coverage of PTV by 95% isodose line.	The average percent difference of the five treatments represents approximately what percent of the total planned prescription was delivered to the target. Under-dosing of the tumor due to organ

[motion may regult in
		motion may result in
		decreased tumor control.
To quantify the deviation in dose	Average percentage	The average percent

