6.3 Chemotherapy Guidelines

Chemotherapy will be given as per standard of care and should begin 2 to 4 weeks after completion of radiotherapy. Recommended total neoadjuvant chemotherapy regimens are:

- CAPOX (capecitabine/oxaliplatin)
- FOLFOX (oxaliplatin, leucovorin, and 5-FU)
- FLOT (docetaxel, oxaliplatin, leucovorin, and 5-FU)

However, the treating medical oncologist may prescribe other SOC total neoadjuvant chemotherapy regimen upon discussion with the WUSM PI. Additionally, if one regimen is not tolerated, subjects can move between regimens for a goal of 4 months of chemotherapy treatment total prior to surgery.

Patients who are unable to complete their total neoadjuvant therapy regimen may complete the chemotherapy postoperatively, at the discretion of the treating physician. Postoperative chemotherapy should start within 3 months of surgery. Patients who are medically inoperable will continue to receive chemotherapy until the entire regimen is complete.

A maximum (cumulative) delay of treatment of 4 weeks (or single delay of 3 weeks) is allowed per protocol due to factors/AEs listed in Section 7.0 (i.e., chemotherapy should be completed within a 5-month period). Cumulative delays in excess of 4 weeks, or single delays in excess of 3 weeks, will need to be discussed with the Principal Investigator in regard to proceeding to surgical resection. Such cases will need to be individualized depending on the clinical scenario. Please note that chemotherapy administration and AE assessment should be performed under the supervision of a medical oncologist. Dosing is to follow standard of care recommendations per institutional guidelines.

Interval imaging during chemotherapy, if obtained, is at the discretion of the treating physician.

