6.6 Definitions of Evaluability

Local control rate at 1 year post RT	Have received at least one fraction of
	radiation therapy and undergone at
	least one disease assessment
Rate of grade 3 or greater toxicity	Have received at least one fraction of
Rate of grade 5 of greater toxicity	
	radiation therapy
Overall survival at 1 year post RT	Have received at least one fraction of
	radiation therapy
Disease-free survival at 1 year post RT	Have received at least one fraction of
	radiation therapy and undergone at
	least one disease assessment
Exploratory	
Average percent difference in coverage of	Have received at least one fraction of
PTV by 95% isodose line	radiation therapy
Average percentage difference in dose to	Have received at least one fraction of
nearby OARs due to variation in OAR	radiation therapy
position	
Percentage of patients in each TCGA	Have completed radiation therapy and
molecular subtype after radiation and	neoadjuvant chemotherapy
chemotherapy	
Specific biomarkers	Have had specimens collected for
·	biomarkers
ctDNA	Have had specimens collected for
	biomarkers

Note that inevaluable patients will not be replaced.

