10.1 Adverse Event Collection in the Case Report Forms

All adverse events that occur beginning with start of treatment (minus exceptions defined in Section 8.0) must be captured in the Toxicity Form. Baseline AEs should be captured on the Medical History Form.

Participant death due to disease progression should be reported on the Toxicity Form as grade 5 disease progression. If death is due to an AE (e.g. cardiac disorders: cardiac arrest), report as a grade 5 event under that AE. Participant death must also be recorded on the Death Form.

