14.3 Analysis of Secondary Endpoints

Secondary endpoints include the following:

- The proportion of patients that can complete total neoadjuvant chemotherapy.
- The local control rate at 1 year will be described as percent with 95% confidence interval. Local control is defined as no local recurrence, calculated from RT start.
- The rate of grade 3 or higher toxicity will also be described as percent with 95% confidence interval.
- Kaplan-Meier estimates will be used to describe disease-free survival (no cancer evident or death) and overall survival (survival from start of RT) at 1 year.

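### The Section 8.0 recording exception leaves some possibly radiation-related events off the Toxicity Form, so the grade 3+ rate may be understated

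*Combined protocol and SAP*

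**What the plan says.** Section 8.0 sets the window: "Adverse events will be tracked from baseline through 12 months after surgery", or 12 months after the definitive end of treatment for patients without surgery. It then gives the general rule, "All adverse events must be recorded on the toxicity tracking case report form (CRF) with the exception of" two classes. The first is baseline events, which go to the medical history form. The second is events "thought to be at least possibly related to a non-protocol treatment received after the patient comes off SCRT or neoadjuvant chemotherapy". No other form is named for this second class.

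Section 10.1 carries the rule into data collection: events from the start of treatment "minus exceptions defined in Section 8.0) must be captured in the Toxicity Form".

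The endpoint in Section 3.0 is "The rate of grade 3 or greater toxicity as defined by CTCAE v 5.0". Section 14.3 adds only: "The rate of grade 3 or higher toxicity will also be described as percent with 95% confidence interval". Neither place has an attribution rule or a step for excepted events. Under Section 6.6 a patient counts after one fraction of radiation, and "Note that inevaluable patients will not be replaced".

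Three other places bear on who could be affected. Section 6.9 keeps patients who stop treatment early in follow-up. Section 6.4 leaves further treatment to the physician when the permanent margin proves positive. Section 6.3 says: "Patients who are unable to complete their total neoadjuvant therapy regimen may complete the chemotherapy postoperatively".

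**The concern.** Possible relation is a low bar for attribution, and here it is applied to one side only. Read literally, a grade 3 event judged probably due to radiation and possibly due to a later drug is left off the form. The later treatment need only be a possible cause, however likely the protocol treatment is.

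Section 3.0 justifies the toxicity endpoint by the possibility that adding radiation makes treatment more toxic. Events with an uncertain cause during follow-up bear on that question, and the rule removes them before analysis. The worst-grade toxicity tables for the monitoring board (Section 12.0) have the same gap if they are built from this form. Because non-protocol treatment is not defined, sites could also classify the same event differently.

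**Working it through.** **1. Does another passage restore the event?**

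| Place | What it does with an event that has both a protocol and a later possible cause |
|---|---|
| Section 8.0 | Keeps it off the toxicity form; names no alternative |
| Section 10.1 | Repeats the exception for the Toxicity Form |
| Section 10.0 schedule | Lists no other general adverse-event form |
| Section 14.3 | No analysis rule that adds it back |
| Section 8.3 | Serious events go to the coordinating principal investigator within 24 hours; exception not repeated |
| Section 10.1, deaths | A death due to an adverse event is entered as grade 5; exception not repeated in that sentence |
| Section 8.4 | Events exempt from expedited reporting must still be captured electronically; this concerns expedited reporting and does not clearly override Section 8.0 |

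So grade 5 events and serious events have another route. Non-serious grade 3-4 events have none that the plan names.

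**2. Can the rule operate in the window?** Yes. Follow-up continues after treatment stops (6.9), later discretionary treatment is foreseen (6.4), and tracking runs 12 months past surgery or the end of treatment (8.0).

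**3. The plan's own figure.** None is given for toxicity. The only computed figure in Section 14.0 is the interval of 9% to 37% for a pathologic complete response rate of 20% with 36 patients. The exact (Clopper-Pearson) method at 0.20 × 36 = 7.2 gives 8.6% to 36.7%, which reproduces it. This point does not change that figure. The same method is used below.

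**4. Effect on the toxicity rate.** Take the rate as the share of evaluable patients with at least one grade 3+ event; the plan does not spell this out. Let n = 36 (the maximum, from Sections 2.3.1 and 6.6), T the number of patients with a grade 3+ event in the window, and k the number whose only such event is excepted.

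Observed rate = (T − k)/n. Loss = k/n. One patient: 1/36 = 2.8 points. Four patients: 4/36 = 11.1 points.

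Since k cannot be negative, the observed rate never exceeds T/n. T and k below are assumed, because the documents give neither an expected toxicity rate nor the share of patients with later treatment.

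| T | k = 0 | k = 1 | k = 2 | k = 4 |
|---|---|---|---|---|
| 11 | 30.6% (16.3 to 48.1) | 27.8% (14.2 to 45.2) | 25.0% (12.1 to 42.2) | 19.4% (8.2 to 36.0) |
| 18 | 50.0% (32.9 to 67.1) | 47.2% (30.4 to 64.5) | 44.4% (27.9 to 61.9) | 38.9% (23.1 to 56.5) |

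Brackets are exact 95% intervals. If no patient has later non-protocol treatment, or every affected patient already has another recorded grade 3+ event, k = 0 and nothing is lost.

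**The case against.** The exception has a legitimate purpose. Counting every event during later therapy could overstate the toxicity of the studied regimen. The endpoint is secondary and descriptive, with no threshold, and the early stopping rules in Section 6.1 use treatment-related deaths, not the grade 3+ rate. One lost patient moves the estimate by 2.8 points, when the interval around 11/36 already runs from 16.3% to 48.1%. All of this stands and limits the consequence. It does not justify leaving off an event that protocol treatment may have caused, because the same purpose is met by excluding only events judged unrelated to protocol treatment.

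Three stronger inferences are tempting, and the documents do not support them.

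- A reader might take the rectal-cancer chemotherapy compliance of 50% to 80% in Section 2.2.2 and infer that 20% to 50% of 36, about 7 to 18 patients, are exposed to the rule. That requires postoperative completion chemotherapy to be non-protocol treatment. Sections 6.0 and 6.3 provide for it, 6.3 gives its timing, and the Section 1.0 schedule marks chemotherapy at the 3-month visit, so the natural reading is the opposite. The 50% is also the comparator, not the total neoadjuvant approach. Completing chemotherapy later is optional, and exposure is not a lost event.
- A reader might infer that the losses fall mainly on patients who tolerated treatment poorly. No passage says so; Section 6.4 foresees further treatment because of margin status.
- A reader might infer that excepted events are lost altogether. Serious events and deaths have the routes shown above.

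**Conclusion.** The point holds as a defect in the recording rule. Followed literally, Sections 8.0 and 10.1 keep dual-cause events off the Toxicity Form, and nothing in Section 14.3 restores them. The grade 3+ rate may therefore be understated, chiefly through non-serious grade 3-4 events.

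The size is unknown and may be zero. The only firm figure is 2.8 points for each patient whose sole grade 3+ event is excepted, assuming 36 evaluable patients; with fewer, the step 1/n is larger. The downward direction is certain only against the rate of all grade 3+ events in the stated window, which is how the endpoint reads, since it has no attribution filter. Against a rate of toxicity caused by radiation alone, the documents do not settle the net direction. The change is worth making because it is cheap and protects a safety endpoint.

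**What to change.** - In Section 8.0, limit the second exception to events judged unrelated to SCRT, protocol chemotherapy and surgery. Section 10.1 then follows by reference.
- Define non-protocol treatment. State that postoperative completion chemotherapy under Section 6.3 is not non-protocol treatment for this rule, or reconcile Sections 6.0, 6.3 and 8.0.
- Record all other events on the Toxicity Form, with separate attribution to SCRT, chemotherapy, surgery and later treatment.
- In Section 14.3, report the grade 3+ rate with and without events that also have a later non-protocol treatment as a possible cause, each with its 95% confidence interval.

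The cost is a wording change, a few attribution fields and some additional form entries. The stated toxicity rate may come out slightly higher. The sample size and the primary analysis do not change. The amendment is best made while events are still being collected, because a non-serious event kept off the form would otherwise have to be sought in source records.

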8.1 WU PI Reporting Requirements

8.1.1 Reporting to the Human Research Protection Office (HRPO) at Washington University

Reporting will be conducted in accordance with Washington University IRB Policies.

Pre-approval of all protocol exceptions must be obtained prior to implementing the change.

8.1.2 Reporting to the Quality Assurance and Safety Monitoring Committee (QASMC) at Washington University

The WUSM PI (or designee) is required to notify the QASMC of any unanticipated problems involving risks to participants or others occurring at WU or any BJH or SLCH institution that has been reported to and acknowledged by HRPO. (Unanticipated problems reported to HRPO and withdrawn during the review process need not be reported to QASMC.)

QASMC must be notified within **10 days** of receipt of IRB acknowledgment via email to [contact]. Submission to QASMC must include the myIRB form and any supporting documentation sent with the form.

For events that occur at secondary sites, the WUSM PI (or designee) is required to notify the QASMC within 10 days of WUSM notification via email to [contact]. Submission to QASMC must include either the myIRB form and supporting documentation or (if not submitted to myIRB) the date of occurrence, description of the event, whether the event is described in the currently IRB approved materials, the event outcome, determination of relatedness, whether currently enrolled participants will be notified, and whether the informed consent document and/or any study procedures will be modified as a result of this event.

8.1.3 Reporting to Secondary Sites

The WUSM PI (or designee) will notify the research team at each secondary site of

all unanticipated problems involving risks to participants or others that have occurred at other sites within **10 working days** of the occurrence of the event or notification of the PI (or designee) of the event. This includes events that take place both at Washington University and at other secondary sites, if applicable. Refer to Section 16.0 (Multicenter Management) for more information

8.2 Secondary Site Reporting Requirements

The research team at each secondary site is required to promptly notify the WUSM PI and designee of all serious adverse events (refer to Appendix B, Section D) within **1 working day** of the occurrence of the event or notification of the secondary site's PI of the event. This notification may take place via email if there is not yet enough information for a formal written report (using FDA Form 3500A (MedWatch) and Washington University's cover sheet (Appendix D)) form if required or an institutional SAE reporting form if not). A formal written report (using FDA Form 3500A) must be sent to the WUSM PI and designee within **4 calendar days** (for fatal or life-threatening suspected adverse reactions) or **11 calendar days** (for serious unexpected adverse reactions) of the occurrence of the event or notification of the secondary site's PI of the event.

The research team at a secondary site is responsible for following its site's guidelines for reporting applicable events to its site's IRB according to its own institutional guidelines.

WUSM research team pre-approval of all protocol exceptions must be obtained prior to implementing the change. Local IRB approval must be obtained as per local guidelines. WUSM IRB approval is not required for protocol exceptions occurring at secondary sites.

8.3 Sub-Investigator Reporting Requirements

All investigators treating patients on this study are responsible for ensuring that serious adverse events (as defined in Appendix B) are reported to the WUSM PI within 24 hours of learning of the event in order for the event to be assessed by the WUSM PI for reporting to HRPO and QASMC.

8.4 Exceptions to Expedited Reporting

Events that do not require expedited reporting as described in Section 8.1 include:

- planned hospitalizations
- hospitalizations < 24 hours
- respite care
- events related to disease progression

Events that do not require expedited reporting must still be captured in the EDC.

9.0 CORRELATIVE STUDIES

9.1 Tissue for Research

Patients with pCR will have normal gastric tissue collected at the time of surgery. Fresh tissue will be formalin-fixed and paraffin-embedded (FFPE) per institutional standards.

RNA and whole exome sequencing will be used for formalin-fixed, paraffin-embedded, post-treatment gastric adenocarcinoma tissue samples to determine the post-treatment patient distribution amongst the TCGA molecular subgroups. Blocks will be reviewed by institutional pathologists, H&E slide prepared to identify the block with highest tumor volume and grade (ideally tumor samples with $\geq 60\%$ tumor nuclei and $\leq 20\%$ necrosis will be processed for nucleic acid extraction³⁸) and then the corresponding block sent for biomarker analysis. Normal tissue adjacent to tumor will also be obtained for differential expression analysis. FFPE tissue will be packaged in insulated Styrofoam packaging and shipped to and sequencing performed at the Washington University Genome Technology Access Center. Cold packs and dry ice are not necessary for FFPE tissue samples. Shipping address is:

Genome Technology Access Center [name]

